- c) Subjects with history of chronic or recurrent bacterial infection (such as chronic pyelonephritis, osteomyelitis, and bronchiectasis etc.) or evidence (as assessed by the Investigator) of active or latent bacterial or viral infections at the time of enrollment, including subjects with evidence of Human Immunodeficiency Virus (HIV) infection.

- d) Subjects with history of recurrent herpes zoster (more than 1 episode) or disseminated (more than 1 dermatome) herpes zoster or disseminated herpes simplex, or ophthalmic zoster will be excluded. Symptoms of herpes zoster or herpes simplex must have resolved more than 60 days prior to screening.
- e) Subjects with history of primary immunodeficiency.
- f) Subjects who have present or previous malignancies, except documented history of cured non-metastatic squamous or basal skin cell carcinoma, or cervical carcinoma in situ, with no recurrence in the 5 years prior to screening. Subjects who had screening procedure that is suspicious for malignancy, and in whom the possibility of malignancy cannot be reasonably excluded following additional clinical, laboratory or other diagnostic evaluations.
- g) Current symptoms of severe, progressive, or uncontrolled renal, hepatic, hematological, gastrointestinal, pulmonary, psychiatric, cardiac, neurological, or cerebral disease including severe and uncontrolled infections, such as sepsis and opportunistic infections. Concomitant medical conditions that, in the opinion of the investigator, might place the subject at unacceptable risk for participation in this study.
- h) Subjects who have received any live vaccines within 3 months of the study drug administration or are scheduled to receive live vaccines during the study. Study subjects should not be administered a live virus vaccine for a minimum of 3 months following the last dose of study medication. Subjects who are in close contact with others who have received a live vaccine may be enrolled at the investigator's discretion.
- i) Subjects who have undergone a major surgical procedure within the 60 days prior to randomization.
- j) Subjects with a known current problem with drug or alcohol abuse history or known cirrhosis including alcoholic cirrhosis.
- k) Subjects who have received prior treatment with abatacept or CTLA4Ig or other CTLA4 therapies.

3. Physical and Laboratory Test Findings

- a) Body mass index (BMI): > 40 in subjects ≥ 18 years of age and $\geq 99\%$ percentile for subjects < 18 years of age.

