- b) Hepatitis B surface antigen (HBsAg)-positive, or Hepatitis B core antibody (HBcAb)-positive subjects with detectable hepatitis B viral DNA
- c) Hepatitis C antibody (HcAb)-positive subjects with detectable hepatitis C viral RNA
- d) Hemoglobin (Hgb) < 8.5 g/dl
- e) White Blood Count (WBC) $< 3,000/\text{mm}^3$ ($3 \times 10^9/\text{L}$)
- f) Platelets $< 100,000/\text{mm}^3$ ($100 \times 10^9/\text{L}$)
- g) Serum ALT or AST > 2 times upper limit of normal.
- h) Evidence of active cardiac or pulmonary disease on chest X-Ray (CXR).
- i) Any test results that, in the opinion of the investigator, might place the subject at unacceptable risk for participation in this study

4. Allergies and Adverse Drug Reaction

- a) Hypersensitivity to abatacept and/or its excipients.

5. Other Exclusion Criteria

- a) Prisoners or subjects who are involuntarily incarcerated. (Note: under certain specific circumstances a person who has been imprisoned may be included or permitted to continue as a subject. Strict conditions apply and Bristol-Myers Squibb approval is required.)
- b) Subjects who are compulsorily detained for treatment of either a psychiatric or physical (eg, infectious disease) illness
- c) Subjects with a history or suspicion of unreliability, poor cooperation, or non-compliance with medical treatment.

Eligibility criteria for this study have been carefully considered to ensure the safety of the study subjects and that the results of the study can be used. It is imperative that subjects fully meet all eligibility criteria.

3.3.3 *Women of Childbearing Potential*

Women of childbearing potential (WOCBP) is defined as any female who has experienced menarche and who has not undergone surgical sterilization (hysterectomy or bilateral oophorectomy) and is not postmenopausal. Menopause is defined as 12 months of amenorrhea in a woman over age 45 years in the absence of other biological or physiological causes. In addition, females under the age of 55 years must have a serum follicle stimulating hormone, (FSH) level > 40 mIU/mL to confirm menopause.

*Females treated with hormone replacement therapy, (HRT) are likely to have artificially suppressed FSH levels and may require a washout period in order to obtain a physiologic FSH level. The duration of the washout period is a function of the type of HRT used. The duration of the washout period below are suggested guidelines and the investigators should use their judgement in checking serum FSH levels.

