5.2.7 Body Mass Index (BMI)

Body mass index (BMI) will be used to exclude subjects who have obesity related glomerulopathy as the primary cause of the subject’s refractory proteinuria. (Exclusion Criteria [Section 3.3.2](#), 3,a) Since BMI may fluctuate due to accumulated edema secondary to severe proteinuria and not be indicative of the role an elevated BMI may have played in the underlying disease process, subjects with an elevated BMI at screening may enroll, at the discretion of the investigator, if the high BMI is due to accumulated edema and the BMI was not known to be elevated at onset of disease. These factors must be documented in the study source documents at randomization.

BMI will be calculated at screening for purposes of checking for the exclusion criteria. For BMI determination in children, follow the 2000 CDC Growth Charts (www.cdc.gov/growthcharts) by age and gender.

For adults, BMI is calculated from the weight and standing height as follows:

$$\text{BMI} = \text{body weight (kg)} \div \text{height (meters)}^2$$

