6.3 Populations for Analyses

Efficacy endpoints will be summarized according to the Intent-to-Treat (ITT) population and safety endpoints will be summarized according to the As-Treated population. These populations are described below along with the Per-Protocol population, Immunogenicity population and the Pharmacokinetic population

6.3.1 *Intent-to-Treat Analysis Population*

The Intent-to-Treat (ITT) Analysis Population is defined to include all subjects randomized into the study for whom Case Report Form (CRF) data indicate that at least one dose of study medication (abatacept or placebo) was administered during the double-blind period.

All subjects who were randomized but never received study medication are to be excluded. Given the blinded nature of this study, it is reasonable to assume that subjects who discontinue prior to the receipt of study medication do so for reasons unrelated to study medication.

Subjects are grouped according to the treatments to which they are randomized by Interactive Response System (IxRS).

ITT Analysis Population is also referred to as ‘All Randomized and Treated Subjects’.

6.3.2 *As-Treated Analysis Population*

The As-Treated Analysis Population contains all subjects for whom CRF data indicate that at least one dose of study medication was administered during double-blind period.

Subjects are grouped according to the treatments to which they are randomized, except in cases where information is available, which indicate that a subject received a different treatment for the entire course of the 16 week double-blind period. In this case, the subject will be presented by the treatment they actually received.

The As Treated Analysis Population will also be referred as ‘All Treated Subjects’.

6.3.3 *Per-Protocol Analysis Population*

The Per-Protocol Analysis Population is defined as a subset of the ITT Analysis Population which excludes subjects who have relevant protocol deviations during the 16 week double-blind period. A programmable list of relevant protocol deviations is provided in [APPENDIX 1](#).

The Per-Protocol Analysis Population will only be used if more than 10% of the subjects in either treatment group have relevant protocol deviations. In such a case, the analysis of the primary efficacy endpoints will be repeated in the Per-Protocol Analysis Population.

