7.2 Study Conduct

Relevant protocol deviations, which could have major impact on the interpretation of the primary efficacy endpoint of the study results, will be identified prior to the unblinding the database for all subjects who are randomized and receive double-blind medication. Relevant protocol deviation criteria are listed in [APPENDIX 1](#).

All relevant protocol deviations, pre-randomization and during double-blind period, will be listed and summarized by treatment arm. The per-protocol analysis population will exclude subjects with at least 1 relevant protocol deviation. Relevant protocol deviations will not be assessed for the OLE analysis.

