APPENDIX 2 RELEVANT PROTOCOL DEVIATIONS

Pre Randomization:

- UPCR < 2.7 at screening.
- eGFR below the following level at screening:
 - 50 for subjects < 18 years (new Schwartz equation).
 - 50 for subjects ≥ 18 years (CKD-EPI equation).
- Body mass index (BMI): > 45 in subjects ≥ 18 years of age and ≥ 99% percentile for subjects < 18 years of age at screening.
- Hemoglobin (Hgb) < 7.0g/dl at screening.
- White Blood Count (WBC) < 2,000/mm³ (2 x 10⁹/L) at screening.
- Platelets < 75,000/mm³ (75 x 10⁹/L) at screening.
- Serum ALT or AST > 3 times upper limit of normal at screening.
- Subjects systemically using any of CS (low dose, prednisone or equivalent at doses ≤ 15mg/day), calcineurin inhibitors (cyclosporine and tacrolimus), MMF and MPA for treatment of TRNS (use for other medical indications [e.g. asthma] is allowed), satisfying any of the following:
 - Started using one of the above agents within 8 weeks of enrollment.
 - Not using the standard dose or
 - Have not been on stable dose for at least 4 weeks prior to randomization.

Post Randomization:

- FSGS or MCD diagnosis not confirmed by a pathology report.
- Use of prohibited medication:
 - Any systemic immunosuppressive or immunomodulator per protocol including, but not limited to cyclophosphamide, methotrexate, belimumab, azathioprine, leflunomide, rituximab, experimental therapies, everolimus, sirolimus, corticotropin injection gel (ACTH) or plasmapheresis.
 - Combined use of two or more renin-angiotensin system (RAS) inhibitors.
- Missed two or more doses of investigational product for any reason during double-blind period.

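### The SAP's BMI deviation item has no exception for subjects whom Protocol 5.2.7 lets enroll with oedema-driven high BMI, so every such child, and any such adult above 45, is coded as a relevant deviator

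*SAP*

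**What the plan says.** Protocol 3.3.2, item 3a, sets the exclusion for adults, "Body mass index (BMI): > 40 in subjects" aged 18 or over, and puts the limit for younger subjects at the 99th percentile. The section closes: "It is imperative that subjects fully meet all eligibility criteria".

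Protocol 5.2.7 cites item 3a and gives its purpose, which is to keep out obesity-related glomerulopathy. It then makes an allowance: "subjects with an elevated BMI at screening may enroll, at the discretion of the investigator, if the high BMI is due to accumulated edema". A further condition is that BMI was not known to be high when the disease began. The record required is: "These factors must be documented in the study source documents at randomization".

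SAP Appendix 2, under its pre-randomization heading, has one BMI item with two cuts. The adult cut reads: "Body mass index (BMI): > 45 in subjects ≥ 18 years of age". The cut for children is a BMI of "≥ 99% percentile for subjects < 18 years of age at screening". The item does not mention oedema or Protocol 5.2.7.

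SAP 6.3.3 says how the list is used: "A programmable list of relevant protocol deviations is provided in" an appendix. The per-protocol set is analysed only if more than 10% of either arm has relevant deviations, and then only for the primary endpoint. SAP 7.2 adds: "All relevant protocol deviations, pre-randomization and during double-blind period, will be listed and summarized by treatment arm". It also removes from the per-protocol set anyone with one or more such deviations.

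**The concern.** A relevant deviation should mark a departure from the protocol that matters for the primary endpoint; SAP 7.2 describes it as one that could have a major impact on interpretation. A child enrolled under the 5.2.7 allowance has followed the protocol as 5.2.7 applies it. The SAP nevertheless tests the raw screening BMI by program and has no way to recognise the allowance.

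Three outputs are at stake. The by-arm deviation summary would report compliant subjects as deviators. The 10% trigger would count them. The per-protocol repeat, if run, would leave them out for a reason that has nothing to do with adherence.

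**Working it through.** **Step 1: the texts side by side.** This is mainly a comparison of rules.

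| Subject | Protocol 3.3.2, item 3a, alone | With Protocol 5.2.7 (oedema, not known high at onset, documented) | SAP Appendix 2 |
|---|---|---|---|
| Under 18, at or above 99th percentile | excluded | may enroll | flagged |
| Adult, above 40 and up to 45 | excluded | may enroll | not flagged |
| Adult, above 45 | excluded | may enroll | flagged |

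The allowance states no upper BMI limit and applies to all ages. In children the SAP cut and the exclusion limit coincide, so any child who needs the allowance meets the SAP item. In adults the SAP adds a margin of 45 − 40 = 5 BMI units, so only allowance users above 45 are caught. One consequence is uneven: an adult enrolled at 42 in breach of item 3a is not flagged, while a child enrolled correctly under 5.2.7 is.

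**Step 2: is the missing pediatric margin deliberate?** Most numeric limits in Appendix 2 are looser than eligibility: UPCR 2.7 against 3, hemoglobin 7.0 against 8.5 g/dl, WBC 2,000 against 3,000, platelets 75,000 against 100,000, ALT or AST 3 against 2 times the upper limit, adult BMI 45 against 40. Pediatric BMI has neither a margin nor the exception, and no reason is given. (The eGFR limit, 50 against 45, also departs from the pattern and is a separate matter.)

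**Step 3: do pre-randomization items count?** SAP 6.3.3 and Protocol 8.2 define the per-protocol set by deviations during the 16-week double-blind period. Read literally, that does not reach a screening BMI. SAP 7.2 expressly includes pre-randomization deviations, and Appendix 2 has a section for them. The second reading fits the SAP as a whole, but the wording should agree.

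**Step 4: the trigger.** SAP Section 5 plans 90 subjects at 1:1, so 90 / 2 = 45 per arm. That figure reproduces: for 40% against 12%, two-sided 5%, with continuity correction, the required size is 45 per arm, and power is Φ[(0.28 − 1/45 − 1.96 × √(0.26 × 0.74 × 2/45)) / √(0.40 × 0.60/45 + 0.12 × 0.88/45)] = Φ(0.873) = 80.9%, against the stated 80% or so. If all 45 are treated, 4/45 = 8.9% and 5/45 = 11.1%, so 5 flagged subjects in one arm, counting all deviation types, start the per-protocol analysis. Each subject flagged only for an allowed BMI supplies one of the five.

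**Step 5: scale.** The documents give no rate for any deviation. If the chance that a subject has some relevant deviation were 2%, 5% or 10% (assumed, and independent across subjects), the chance that at least one arm reaches 5 would be 0.4%, 14% or 72%. How much of that would come from allowed high BMI cannot be derived from the documents.

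**The case against.** The strongest reply is that little depends on this. ITT is the primary population, the per-protocol set is conditional, and it serves only to repeat the primary endpoint. No primary estimate or p-value, no secondary endpoint and no safety table changes. That stands, and it limits the weight of the point.

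A second reply is that a sponsor may reasonably keep an objective BMI cut in a supportive analysis. The allowance rests on investigator judgement and on BMI not being known to be high at onset, which a subject with no recorded onset BMI would satisfy. It permits enrollment; it does not prove that obesity played no part. This is fair, but the SAP gives no such reason, and the adult margin shows that a strict cut was not the general approach.

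A reader might also infer that the rule strips out the most oedematous children and leaves a less severe per-protocol population. The documents do not support that. BMI percentile is not a grade of oedema: a severely oedematous child below the 99th percentile stays in, and a moderately oedematous child with a high dry weight goes out. Nothing in the documents links BMI percentile to baseline UPCR or to response.

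Finally, item 3a is not left unqualified, since 5.2.7 names it. The missing reverse reference in 3.3.2 is editorial.

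**Conclusion.** The mismatch holds as a matter of text. The listed rule classes as relevant deviators some subjects whom the protocol lets in: every child enrolled under 5.2.7, and adults so enrolled only above 45. It affects the deviation summary, the count toward 5 of about 45 in an arm, and membership of a per-protocol set that may never be analysed. It does not affect the ITT primary result.

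The conclusion rests on SAP 7.2 governing over the narrower time wording in 6.3.3, and the figure of 5 rests on about 45 treated subjects per arm. The number affected is not given and may be zero, so no share of the trigger can be attributed to this item, and a directional bias in the per-protocol result cannot be claimed. It is worth correcting because the rule is wrong as written and cheap to change.

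**What to change.** In the BMI item of SAP Appendix 2, add: *and no documented exception under Protocol 5.2.7*. Capture the exception as a data flag and settle it before unblinding, when SAP 7.2 already requires relevant deviations to be identified. If the sponsor does want these subjects out of the per-protocol set, the SAP should say so and give the reason.

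Align SAP 6.3.3 with SAP 7.2 on whether pre-randomization deviations count. In the same edit, correct the pointers in both sections: they send the reader to Appendix 1, but the list is in Appendix 2.

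A reference to 5.2.7 in Protocol 3.3.2, item 3a, is an optional editorial change.

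The cost is one clause, one wording alignment and one flag. The flag is the only real work: 5.2.7 requires source documentation only and the documents show no CRF field for it, so sites would have to supply it for each subject above the BMI cut.

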APPENDIX 3 CLINICAL REPORTS CONTENT

Table 9-2: Safety Analysis by Period

	End of Double-Blind	End of Study	
	Period CSR	CSR	
	Double-Blind Period	Cumulative Abatacept Safety Period	OLE Period
Serious Adverse Events	X	X	X
AEs leading to study drug discontinuation	X	X	X
AEs related to study drug	X	X	X
Related events categorized by intensity	X	X	X
Most common related AEs (reported in at least 2% of subjects in any treatment group)	X	X	X
All AEs (serious or non-serious)	X	X	X
AEs by intensity	X	X	X
Most common (serious or non-serious) AEs (reported in at least 5% of subjects in any treatment group)	X	X	X
Serious adverse events and related serious adverse events with death as an outcome (EudraCT)		X	
AEs of Special Interest (Renal Related Events, Infections, Malignancy, Autoimmune Disorder, Infusional Reactions)	X	X	
Multiple Adverse Events	X	X	
EudraCT summaries - Exposure adjusted summaries		X	
Laboratory abnormalities	X	X	X
Laboratory Shift Tables	X	X	X
Mean Change from Baseline in Lab Parameters	X		
Vital Signs	X		X
Immunogenicity	X	X
